6.2 Preparation/Handling/Storage/Accountability

6.2.1 Acquisition and accountability

The Investigator or designee must confirm appropriate temperature conditions have been maintained during transit for all investigational product received and any discrepancies are reported and resolved before use of the investigational product.

The Investigator, institution, or the head of the medical institution (where applicable) is responsible for investigational product accountability, reconciliation, and record maintenance (i.e., receipt, reconciliation, and final disposition records).

6.2.2 Product Storage and Stability

All investigational product must be stored in a secure, environmentally controlled, and monitored (manual or automated) area in accordance with the labeled storage conditions with access limited to the Investigator and authorized site staff.

Further guidance and information for the final disposition of unused investigational products are provided in the Pharmacy Manual.

6.3 Measures to Minimize Bias

This is a randomized, double-blinded, PBO-controlled study. Patients should be randomized as close as possible to the time of the planned first dose of study treatment.

Randomization will be conducted via an interactive web response system (IWRS) in a 1:1:1 ratio for patients to receive BOS-589 200 mg, BOS-589 50 mg, or PBO. Patients will be assigned to the treatment arms using a permuted block randomization stratified by site (44 patients per group). The randomization schedule will be generated by the Study Biostatistician and will be transferred to the IWRS team for loading into the system. The randomization file will be held by the Study Biostatistician until the end of the trial and when the database has been locked.

The sponsor, site staff, and patients will be blinded to the treatment assignment. BOS-589 and PBO will be similar in appearance, and provided in white, opaque, high-density polyethylene (HDPE) bottles, each with a child-resistant closure. Each bottle will be labeled as per country requirement.

Only in a medical emergency will a patient's treatment assignment be unblinded, and this process will be performed and documented in the IWRS. Every effort should be made to contact the Medical Monitor to discuss unblinding prior to breaking the blind.

6.4 Dosing and Administration

Only patients enrolled in the study may receive investigational product and only authorized site staff may supply or administer investigational product.

Eligible patients will be randomized (1:1:1) to receive for a total of 4 weeks BOS-589 at 1 of 2 dose levels or PBO bid. Patients will be randomized to the following cohorts:

- Cohort 1 (High Dose): 2 x 100 mg tablets for the 200 mg BOS-589 bid orally
- Cohort 2 (Low Dose): 2 x 25 mg tablets for the 50 mg BOS-589 bid orally
- Cohort 3 (PBO): 2 x visually matched PBO tablets bid orally

For each dose level and at each dosing timepoint, the 2 tablets are to be swallowed with approximately 240 mL room temperature water and are to be swallowed whole (i.e., not divided, crushed, dissolved, or chewed). On days when postdose PK blood samples are to be taken (see footnote f in the Schedule of Activities, [Section 1.3](#), patients will be asked to refrain from consumption of food and water for 1 hour prior to and for 2 hours after administration of investigational product. Food and water may be consumed *ad libitum* at all other times during the study.

Patients will be instructed to take the investigational product approximately every 12 hours at approximately the same time each day. If a patient misses a dose at a given timepoint, and the time is within 4 hours of the regularly scheduled dosing time, the patient should be instructed to take the investigational product. If it has been longer than 4 hours, the patient should skip the missed dose at that timepoint and resume the regularly scheduled dosing schedule at the next scheduled timepoint.

In the event of vomiting following administration, BOS-589 should not be taken until the next scheduled dose.

6.5 Dose modification

Study treatment should be interrupted if the patient reports any treatment-related severe AE. Therapy should only be restarted after approval by the Medical Monitor.

If therapy is restarted, the same dose should be administered as that prior to occurrence of the AE. If the patient is still having tolerability issues and an AE reoccurs, the dose may be reduced from 2 tablets of study treatment bid to 1 tablet of study treatment bid, without breaking the study blind.

If another AE occurs after the study treatment dose reduction, study treatment will be permanently discontinued and the subject followed until the end of the study.

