¹Should any of these events occur, a full evaluation of other causes of liver enzyme elevation should be undertaken and patients would be followed at regular intervals until labs return to normal/stabilize, or an alternate diagnosis is confirmed.

²If patients develop asymptomatic elevations of the ALT of > 3x ULN and, if there are persistent elevations upon repeat testing, close observation should be implemented, and discontinuation of the drug should be considered.

Depending on the nature, severity, and outcome, the Sponsor will decide to (and document with supporting rationale) either: 1) discontinue study drug; 2) request additional safety data; or 3) continue dosing at current dose or reduced dose (see [Section 6.5](#)).

If 2 or more patients experience any of the above criteria (note: study drug-related SAEs must be in the same system organ class) the study enrollment will be halted. The Sponsor, an independent GI physician not involved with the study, and the lead

investigator will review available data to determine whether individual patient unblinding is warranted, amendments are required for the protocol, and whether patients currently on treatment should also discontinue study drug. A decision to continue (with or without modifications) or discontinue the study will be made. All supporting rationale will be documented.

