8.5.1 Definition of Adverse Events

An AE is any untoward medical occurrence in a patient or clinical study participant, temporally associated with the use of investigational product, whether or not considered related to the investigational product. An AE can therefore be any unfavorable and unintended sign (including an abnormal laboratory finding), symptom, or disease (new or exacerbated) temporally associated with the use of investigational product.

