9.1. Adverse Events

AEs starting after the informed consent date until the Day 43/End of Study Follow-up visit will be recorded. AE assessments will include severity (mild, moderate, severe), relationship to study drug (related or not related), and seriousness. AEs with a missing severity will be classified as severe. AEs with a missing causality will be classified as related. AEs with missing seriousness will be classified as serious.

Any event reported on the CRF that occurs on or after the initiation of study drug is defined as a treatment-emergent adverse event (TEAE). Guidelines for categorizing an event as treatment-emergent based on start and stop dates and times are in Appendix 1. Additionally, an AE that is reported to have started on Day 1 without an associated onset time will be assumed to have occurred after the initiation of study drug. Hence, AEs occurring on Day 1 with no associated onset time will be assumed to be treatment emergent. SAEs associated with a protocol specified procedure and occurring after the time of consent but before administration of first dose of study drug will be defined as non-treatment emergent AEs (NTEAEs) and will be excluded from summary tables but will appear in listings flagged as NTEAE.

On a summary table, the number and percentage of patients in each of the following categories will be summarized by cohort following the cohort display in section 5.9:

- Any TEAE
- Any TEAEs related to study drug
- Any moderate or severe TEAEs
- Any moderate or severe TEAEs related to study drug
- Any treatment-emergent SAEs
- Any treatment-emergent SAEs related to study drug
- Any TEAEs causing discontinuation of study drug
- Any TEAEs with outcome of death
- Any TEAEs leading to withdrawal from the study

AEs will be coded to a SOC and PT using MedDRA (the version used will be defined in the study data management plan).

For summaries of TEAEs by SOC and PT, a patient will be counted once within an SOC, even if the patient experienced more than one TEAE within a specific SOC (likewise for PT). TEAEs will be ordered by descending frequency for overall SOC incidence followed by descending frequency of overall PT incidence. Summaries of TEAEs by SOC and PT will include the following:

- All TEAEs
- All TEAEs by severity
- All moderate or severe TEAEs
- All TEAEs related to study drug
- All treatment-emergent SAEs

Sponsor: Boston Pharmaceuticals, Inc.
Protocol Number: BOS-589-201
Version and Date: Version 1.2 12NOV2020

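### Protocol Sections 6.5 and 7.2 are not reconciled on restart dose and decision-maker where their triggers overlap, and the final stopping step of 6.5 names an AE with no severity or relatedness qualifier

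*Protocol*

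**What the plan says.** Protocol Section 6.5 sets out a sequence of steps. Entry: "Study treatment should be interrupted if the patient reports any treatment-related severe AE". Permission to resume: "Therapy should only be restarted after approval by the Medical Monitor". Dose on resuming: "If therapy is restarted, the same dose should be administered as that prior to occurrence of the AE". If tolerability problems persist and an AE comes back, the dose may go from two tablets to one at each twice-daily intake. Last step: "If another AE occurs after the study treatment dose reduction, study treatment will be permanently discontinued".

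Protocol Section 7.2 lists events that require immediate suspension: any drug-related SAE, four days without a bowel movement, several serious gastrointestinal findings, and liver criteria. It continues: "Depending on the nature, severity, and outcome, the Sponsor will decide to" take one of three courses, with a documented rationale. These are to stop the drug, to ask for more safety data, or to "continue dosing at current dose or reduced dose". The third course refers the reader to Section 6.5.

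Three other places bear on this. Section 8.5.1 counts an event as an AE "whether or not considered related to the investigational product". The severity scale in 8.5.4.1 starts at mild. Section 3 of the protocol and Section 2 of the SAP name AE-led discontinuations as part of the primary safety endpoint, and SAP 9.1 tabulates them by cohort in the row "Any TEAEs causing discontinuation of study drug".

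**The concern.** Two sections deal with treatment held for a drug-related event and then possibly resumed. They name different decision-makers and permit different doses, and the cross-reference from 7.2 to 6.5 does not lead to the rule that 7.2 seems to rely on. A patient who meets both triggers has two procedures to follow, and nothing says which governs or how they combine. The question arises after a serious event, when the instruction should be clear.

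The second part concerns the steps within 6.5. The way in is narrow (severe and treatment-related). The way out is wide (any further AE) and mandatory. If the last step is applied as written, a dose-reduced patient could lose treatment, and be counted as an AE-led discontinuation, for an event that says nothing about tolerability. If some investigators read it literally and others read it in context, that component of the primary safety endpoint is not defined in the same way across sites. The trial is meant to inform dose selection, so tolerability by dose should mean one thing.

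**Working it through.** No figure in the plan needs reproducing. The check compares passages of the current protocol (v3.0), with a little arithmetic on dose and on the endpoint.

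**Do the triggers overlap?** Section 8.5.4.1 separates severity from seriousness and says that an SAE may also be rated severe. A drug-related SAE rated severe therefore meets the entry condition of 6.5 and a listed condition of 7.2. The overlap is partial: a severe related AE that is not serious and not otherwise listed falls under 6.5 only, and four days without a bowel movement may fall under 7.2 only.

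**What each section says about that patient**

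| Question | Section 6.5 | Section 7.2 |
|---|---|---|
| Who decides on resuming | Medical Monitor approves; Sponsor not mentioned | Sponsor decides and documents; Medical Monitor not mentioned in this decision |
| Dose at first restart | Same as before the event | Current or reduced |
| When a reduction is open | After a restart, if an AE comes back | After the first event, with a pointer to 6.5 |

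**Does the pointer resolve it?** The only route to a reduction in 6.5 runs through a restart at the same dose followed by a recurrence. A reader sent there from 7.2 after a first event finds no provision for reducing at that stage.

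**Size of the dose difference.** By Section 6.4, Cohort 1 takes 2 x 100 mg = 200 mg bid and Cohort 2 takes 2 x 25 mg = 50 mg bid. One tablet bid is 100 mg or 25 mg. The ratio is 2 in each cohort.

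**Condition at each step of 6.5**

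| Step | Event required | Severity stated | Relatedness stated |
|---|---|---|---|
| Interrupt | AE | Severe | Treatment-related |
| Reduce (optional) | An AE that comes back, with continuing tolerability issues | No | Only by implication |
| Stop permanently (mandatory) | A further AE | No | No |

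With the definition in 8.5.1 and the scale in 8.5.4.1, the literal condition for the last step includes a mild, unrelated event. There is also a contrast with 7.2, where the Sponsor may continue dosing after a listed suspension event. After a reduction, 6.5 leaves no such choice for any AE.

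**Effect on the endpoint.** With 44 patients per cohort (Section 4.1.2), and if all are treated, one extra stop changes that cohort's discontinuation incidence by 1/44 = 0.0227, or 2.3 percentage points. The number of such stops cannot exceed the number of dose-reduced patients, which the documents do not forecast.

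**Likely source.** Section 7.2 of protocol v1.0 had no suspension list and no Sponsor decision. Both appear in v2.0, while the text of 6.5 is the same in v1.0, v2.0 and v3.0. The newer procedure seems to have been added without revising the older one.

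**The case against.** The best reply is that the sections can be followed together. The current dose is among the options in 7.2 and is what 6.5 prescribes, so a same-dose restart with both the Medical Monitor's approval and a documented Sponsor decision satisfies both. The reduced-dose option cites 6.5 and can be read as subject to its sequence. This is sound, and a reader who infers that the rules are opposite, or cannot both be obeyed, goes further than the text. What remains is that 7.2 on its face offers a first-restart option that 6.5 does not contain, and neither section says that both approvals are needed.

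A reader might also infer that sites could re-expose similar patients at different doses on their own judgment. The documents do not support that: the decision lies with the Medical Monitor in one section and the Sponsor in the other.

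On the last step of 6.5, it can be argued that the sequence is about tolerability, so a further AE means a further tolerability event. That is a reasonable reading in context, but the sentence does not say so and its instruction is mandatory. The ambiguity stands.

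Finally, a reader might infer that the SAP hides patients who could not stay on full dose because it tabulates only discontinuations. It does not. SAP 9.1 also tabulates by cohort related TEAEs, moderate or severe TEAEs (overall and related) and serious TEAEs, so the event that starts the sequence is counted. SAP 6.8 fixes planned tablets at four per day and summarizes actual daily tablets and compliance, so reduced intake shows. For example, 12 of 28 days at one tablet bid gives (16 x 4 + 12 x 2)/(28 x 4) = 88/112 = 78.6%. What the SAP lacks is a row linking an AE to an interruption or reduction, which would be useful but is a matter of preference.

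**Conclusion.** The point holds as an inconsistency and an ambiguity in the current protocol. Where the triggers overlap, 6.5 and 7.2 differ on who decides and on whether a reduction is open at first restart, and the cross-reference does not settle it. The permitted doses can differ by a factor of 2. Separately, the mandatory stop in 6.5 has no severity or relatedness condition, so its literal scope includes mild, unrelated events, which can add to AE-led discontinuations in the primary safety endpoint.

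The number of patients affected is unknown. Reaching the last step takes a related severe AE, an approved restart, a recurrence, a reduction and a further AE, all within 28 days of dosing, so it may be small. The documents give no rates from which to estimate it. The 2.3-point figure per patient assumes 44 treated patients in the cohort. The conclusion rests on the wording and on a possible overlap of triggers, not on any assumed frequency. It does not extend to a claim that tolerability by dose cannot be read from the planned tables, and it implies no view on which dose or stopping rule is right.

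**What to change.** The sponsor must reconcile Sections 6.5 and 7.2 so that one passage states, for each interruption or suspension trigger, who approves resuming and which doses are open at that point, including the case where an event meets both triggers. The cross-reference from 7.2 should then lead to a provision that exists. The last step of 6.5 must state which AEs it refers to, in severity and relatedness. The content of these rules is for the sponsor's clinicians to decide.

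The cost is amended wording in two protocol sections, with no added patients, visits or procedures.

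Optional: rows by cohort in SAP 9.1 for TEAEs leading to interruption and to dose reduction, and a count of dose-reduced patients in SAP 6.8. Section 6.6 of the protocol already has departures from the prescribed regimen recorded in the CRF, so this would mean a few table rows, provided the CRF also records the AE that led to the change.

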6.6 Investigational Product Compliance

All patients in this study will commence therapy on site on Study Day 1; oral investigational product will be administered under clinic staff supervision. After patients are discharged to continue therapy at home, compliance will be assessed on subsequent visits by returned tablet count. Administration of investigational product and any deviation(s) from the prescribed dosage regimen should be recorded in the case report form (CRF) and Drug Accountability Record.

6.7 Concomitant Therapy

Refer to [Appendix 4](#) for more details on which concomitant medications are permitted and which are excluded while patients are on study.

Any prior or concomitant therapy (including over the counter or prescription medicines, vitamins and/or supplements) taken 28 days prior to the first dose of investigational product through the End-of-Study Visit must be recorded, along with:

- Reason for use;
- Dates of administration including start and end dates;
- Dosage information including dose and frequency.

The Medical Monitor should be contacted if there are any questions regarding concomitant or prior therapy.

For this protocol, a prescription medication is defined as a medication that can be prescribed only by a properly authorized/licensed clinician. Medications to be reported in the CRF are concomitant prescription medications, over-the-counter medications, vaccines, vitamins, and supplements.

6.7.1 Rescue Medicine

During the double-blind Treatment Phase of the study, patients will be allowed to take loperamide rescue medication for the acute treatment of uncontrolled diarrhea. It is recommended that patients refrain from loperamide unless a minimum of 2 or more uncontrolled diarrhea events that cause significant discomfort and prevent normal everyday activities are experienced in a given 24-hour period.

If loperamide must be used, patients must not exceed the 2 mg (unit dose), which may be taken once approximately every 6 hours and must not exceed the following dosing requirements:

- No more than 4 unit doses over a continuous 24-hour time period (8 mg/day);
- No more than 7 unit doses over a continuous 48-hour time period (14 mg over 2 days);
- No more than 11 unit doses over a continuous 7-day time period.

The use of loperamide rescue medication should be recorded electronically.

6.8 Intervention After the End of the Study

BOS-589 will not be provided to study patients after the end of the study.

7 DISCONTINUATION / WITHDRAWAL

7.1 Discontinuation of Investigational Product

A patient may discontinue from study treatment at any time at his or her own request or may be withdrawn at any time at the discretion of the Investigator for safety, behavioral, or administrative reasons. Discontinuation from the investigational product does not mean discontinuation from the study, and remaining study procedures should be completed as indicated by the study protocol. If a clinically significant finding is identified (including, but not limited to, changes from baseline) after enrollment, the Investigator or qualified designee will determine if any change in patient management is needed. Any new clinically relevant finding will be reported as an AE.

Upon investigational product discontinuation, patients should complete all procedures collected in the Day 29/End-of-Treatment visit as applicable per the Schedule of Activities ([Section 1.3](#)).

7.2 Discontinuation/Withdrawal from the Study

A patient may withdraw from the study at any time at his or her own request or may be withdrawn at any time at the discretion of the Investigator for the following reasons:

- If any clinical AE, laboratory abnormality, or other medical condition or situation occurs such that continued participation in the study would not be in the best interest of the patient;
- Disease progression that requires discontinuation of the investigational product;
- Pregnancy;
- If the patient meets an exclusion criterion (either newly developed or not previously recognized) that precludes further study participation after consultation with the Medical Monitor;
- Significant investigational product noncompliance;
- Termination of the study by the sponsor.

If the patient withdraws consent for disclosure of future information, the sponsor may retain and continue to use any data collected before such a withdrawal of consent.

If a patient withdraws from the study, he or she may request destruction of any samples taken and not tested, and the Investigator must document this in the site study records.

See Schedule of Activities, Section 1.3, for data to be collected at the time of study discontinuation and follow-up and for any further evaluations that need to be completed.

The reason for patient discontinuation or withdrawal from the study will be recorded on the CRF.

Patients who sign the ICF and are randomized but do not receive the investigational product may be replaced. Once randomized, patients who are withdrawn from therapy before completing 28 days of dosing or are discontinued from the study for any reason will not be replaced.

Clinical and/or laboratory criteria that may warrant study drug discontinuation.

If a patient experiences any of the following clinical or laboratory events, study treatment should be immediately suspended:

- Any SAE considered study drug-related;
- No bowel movement for 4 days;
- Any clinical evidence suggestive severe constipation, obstipation or intestinal obstruction; gastrointestinal hemorrhage, significant gastrointestinal infection;
- Abnormal liver functions concerning for drug-induced as follows¹:
 - Confirmed ALT > 5x ULN
 - Confirmed ALT > 3x ULN and any of the following signs or symptoms (fatigue, nausea, vomiting, right upper quadrant pain, fever, rash or eosinophilia)²
 - Confirmed ALT > 3x ULN and total bilirubin > 2x ULN or INR > 1.5 (**should be repeated in 48-72 hours**)

¹Should any of these events occur, a full evaluation of other causes of liver enzyme elevation should be undertaken and patients would be followed at regular intervals until labs return to normal/stabilize, or an alternate diagnosis is confirmed.

²If patients develop asymptomatic elevations of the ALT of > 3x ULN and, if there are persistent elevations upon repeat testing, close observation should be implemented, and discontinuation of the drug should be considered.

Depending on the nature, severity, and outcome, the Sponsor will decide to (and document with supporting rationale) either: 1) discontinue study drug; 2) request additional safety data; or 3) continue dosing at current dose or reduced dose (see [Section 6.5](#)).

If 2 or more patients experience any of the above criteria (note: study drug-related SAEs must be in the same system organ class) the study enrollment will be halted. The Sponsor, an independent GI physician not involved with the study, and the lead

investigator will review available data to determine whether individual patient unblinding is warranted, amendments are required for the protocol, and whether patients currently on treatment should also discontinue study drug. A decision to continue (with or without modifications) or discontinue the study will be made. All supporting rationale will be documented.

